5.9.3 Permitted Drugs

During the study, unless contraindicated, subjects may take acetaminophen/paracetamol, levodropropizine and chlorpheniramine for symptom relief according to the label's prescribing information and at dosages that do not exceed the manufacturer's recommendations. Those medication for symptom relief would be prescribed by investigators as P.R.N (pro re nata). The investigator should train the subject to administer maximum twice a day as much as possible. And administration of the medication during the study should be reported on the diary. Subject will be not allowed to use other drugs for symptom relief except acetaminophen/paracetamol, levodropropizine and chlorpheniramine.

If these drugs are taken, details concerning the dose and duration of treatment will be recorded in the subject's medical records (source documents) and in the eCRF.

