8.5 Statistical Analyses

8.5.1 Primary Efficacy Analysis

The primary efficacy endpoint analysis will assess the time (in days) from the administration of study drug to resolution of influenza symptoms and fever. This analysis will be performed on the ITTI population. Data will be obtained from responses recorded on the Flu-iiQ™.

Resolution of symptoms has occurred if the following influenza symptoms (as recorded on the Flu-iiQ™) are mild in intensity or none for at least 24 hours.

- Respiratory symptoms (cough, sore throat, and nasal congestion).
- Constitutional symptoms (headache, feeling feverish, body aches and pains, and fatigue).

Resolution of fever is defined as:

- Body temperature of $<37.0^{\circ}\text{C}$ for at least 24 hours. (The start time for resolution of fever is defined as the time recorded in the diary when body temperature was $<37.0^{\circ}\text{C}$ for at least 24 hours.)

If the subject has received the drugs for symptom relief, the effective duration of the drugs for symptom relief should be considered.

For example, the study drug was administered at 12:00 on 1st day. The first time body temperature recorded $<37.0^{\circ}\text{C}$ in the diary was 10:00 on 2nd day and continued more than 24 hours. But acetaminophen/paracetamol known to be effective for 6 hours had been administered at 09:00 on 2nd day [1 hour prior to the time when the body temperature decreased $<37.0^{\circ}\text{C}$], it will be calculated that the start time point for body temperature $<37.0^{\circ}\text{C}$ is 15:00 on 2nd day [27 hours after the study drug administration]. Then, if the next first time body temperature recorded $<37.0^{\circ}\text{C}$ in the diary was 22:00 on 2nd day and body temperature was $<37.0^{\circ}\text{C}$ for 24 hours from then, the start time for resolution of fever is 22:00 on 2nd day [34 hours after the study drug administration].

The primary efficacy endpoint will be analyzed using a Wilcoxon rank-sum test to assess differences between treatment groups, if every subject were followed until resolution of influenza symptoms and fever. The statistically significant difference of time to resolution of influenza symptoms and fever between placebo and CT-P27 based on Wilcoxon rank-sum test will be presented by p-values. If there is any censoring, the primary efficacy endpoint will be analyzed using Log-rank test, and Kaplan-Meier plots will be presented.

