10.1 Primary Efficacy Analysis

The primary efficacy endpoint analysis will assess the time from the administration of study drug to resolution of influenza symptoms and fever. The Flu-iiQ™ and body temperature recorded in diary including records as

Statistical Analysis Plan

a part of suspicious ADE assessment will be used for the analysis. The Flu-iiQ™ is a validated questionnaire with four domains. This includes the Domain 1; intensity of influenza symptoms, Domain 2; impact on activities, Domain 3; effects on feelings and Domain 4; concerns due to influenza. Subjects are offered four choices, ranging from the most positive response (e.g., none or not at all) to the most negative choice (e.g., severe or great difficulty). This analysis will be performed on the ITTI population.

The definitions of resolution of influenza symptoms and fever are described below.

Resolution of symptoms has occurred if all of the following influenza symptoms (as recorded on the Flu-iiQ™ of Domain 1) are mild in intensity or none for at least 24 hours. (4-point scale - 0: None, 1: Mild, 2: Moderate, 3: Severe).

- Respiratory symptoms (cough, sore throat, and nasal congestion)
- Constitutional symptoms (headache, feeling feverish, body aches and pains, and fatigue)

Resolution of fever is defined as:

- Body temperature (as recorded in the diary) of $<37.0^{\circ}\text{C}$ for at least 24 hours.

The start time for resolution of influenza symptom and fever is defined as the start time when symptoms and fever are resolved, whichever occurred latest.

The time (in days) from the administration of study drug to resolution of influenza symptoms and fever will be calculated as follows: [Start date/time of resolution of influenza symptoms and fever] – [Start date/time of study drug administration]. If time of completion of diary for Flu-iiQ™ and body temperature is missing then the time will be assumed to be 10:00 AM and 10:00 PM for Morning and Evening, respectively.

If the subject has received the drugs for symptom relief, the effective duration of the drugs for symptom relief should be considered in determining the start time for resolution of symptom and fever.

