For example, the study drug was administered at 12:00 on 1st day. The first time body temperature recorded $<37.0^{\circ}\text{C}$ in the diary was 10:00 on 2nd day and continued more than 24 hours. But acetaminophen/paracetamol known to be effective for 6 hours had been administered at 09:00 on 2nd day [1 hour prior to the time when the body temperature decreased $<37.0^{\circ}\text{C}$], it will be calculated that the start time point for body temperature $<37.0^{\circ}\text{C}$ is 15:00 on 2nd day [27 hours after the study drug administration]. Then, if the next time body temperature recorded $<37.0^{\circ}\text{C}$ in the diary since 15:00 was 22:00 on 2nd day and body temperature was $<37.0^{\circ}\text{C}$ for 24 hours from then, the start time for resolution of fever is 22:00 on 2nd day [34 hours after the study drug administration].

Drugs for symptom relief will be discussed during blinded DRM (14.5). Only drugs for symptom relief with an effective duration overlapping the primary endpoint duration (from a day of resolution start to resolution end) will be considered as drugs that affect the result of primary efficacy analysis. Effective durations of each drug will be discussed during blinded DRM too.

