14.3.2 Symptom Relief Medication

The start date imputation will follow the same rules applied for the prior and concomitant start dates. The end date imputation will also follow the same rules applied for the prior and concomitant end dates, except that the partial dates will be compared to the dates of Day 8 instead of EOS. For subjects with suspicious ADE, the same rules will be applied, but last date of suspicious ADE assessment will be used instead of Day 8.

To determine the start time for resolution of symptom and fever in primary efficacy analysis, incomplete first and last taken time of symptom relief drug will be imputed as follows:

Route	Frequency	Time of first taken	Time of last taken
Oral Respiratory(Inhalation) Intramuscular Ophthalmic	Once, Daily	08:00	08:00
	BID	08:00	20:00
	TID	08:00	20:00
Intravenous	Once, Daily	08:00	23:59
	BID	08:00	23:59
	TID	08:00	23:59

※ If a symptom relief drug was administered once intravenously and single dose is 2g then missing last taken time will be imputed as the first taken time.

Statistical Analysis Plan

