14.5 Drugs for Symptom Relief and Effective Duration

Drug (PT)	Effective Duration (Hours)
ACETYLCYSTEINE	12
ACTIFED /00005601/	12
BENZDAMINE HYDROCHLORIDE	12
CEFDITOREN PIVOXIL	8
CEFRADINE	12
CHLORPHENAMINE	6
CHLORPHENAMINE MALEATE	6
CODENA-S	8
DESLORATADINE	24
DEXIBUPROFEN	12
DICLOFENAC	24
ELECTROLYTES NOS W/GLUCOSE	0
ERDOSTEINE	12
FLUOROMETHOLONE ACETATE	6
FLUTICASONE FUROATE	24
GLUCOSE	0
LEVOCETIRIZINE DIHYDROCHLORIDE	32
LEVODROPROPIZINE	6
LEVOFLOXACIN	8
MONTELUKAST	24
PARACETAMOL	6 (Single dose : 100 mg, 300 mg, 500 mg, 1000 mg)
	8 (Single dose : 650 mg, 1300 mg)
PETHIDINE	8
PHENIRAMINE	24
PREDNISOLONE	24
PROPACETAMOL HYDROCHLORIDE	12
PSEUDOEPHEDRINE	12

CONFIDENTIAL

Statistical Analysis Plan

HYDROCHLORIDE	
SODIUM CHLORIDE	0
THEOBROMINE	12
TRAMADOL	6
TRAMADOL HYDROCHLORIDE	6
TROPHAMINE /02659801/	0
ZIPEPROL DIHYDROCHLORIDE	12

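### The medication adjustment in the primary endpoint does not link drugs to components, and Appendix 14.5 gives masking windows to antibiotics and fluorometholone, which have no evident effect on either component

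*SAP*

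**What the plan says.** SAP 10.1 makes the event time the later of two resolutions: "defined as the start time when symptoms and fever are resolved, whichever occurred latest". All seven respiratory and constitutional symptoms, and temperature, must meet their criteria for 24 h. It then adds that "the effective duration of the drugs for symptom relief should be considered in determining the start time for resolution of symptom and fever". Protocol 8.5.1 has the parent rule: "If the subject has received the drugs for symptom relief, the effective duration of the drugs for symptom relief should be considered". Neither text links a drug to a component. The only worked example, shared by both documents, is paracetamol with a 6 h duration applied to temperature.

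A drug enters the rule when the eCRF marks it as used for symptom relief (SAP 9.3). The one stated filter is timing: "Only drugs for symptom relief with an effective duration overlapping the primary endpoint duration" are treated as affecting the result. The list and durations go to the blinded data review meeting, with no criterion for keeping or removing a drug.

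Appendix 14.5 lists 32 entries, each with a duration and none with a target symptom. For the primary analysis, Appendix 14.3.2 says "incomplete first and last taken time of symptom relief drug will be imputed as follows"; its table has an ophthalmic route and places twice-daily doses at 08:00 and 20:00. Protocol 5.9.3 states: "Subject will be not allowed to use other drugs for symptom relief except acetaminophen/paracetamol, levodropropizine and chlorpheniramine".

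**The concern.** The adjustment is meant to stop a drug-suppressed reading from counting as recovery. That makes sense only where the drug can suppress what is being read. Appendix 14.5 already uses 0 h for four fluids or nutrients, so a non-masking category exists. It was not used for three antibiotics, although SAP 10.2 and Appendix 14.4 treat antibiotics as therapy for secondary complications, nor for "FLUOROMETHOLONE ACETATE".

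A subject who is well but taking one of these drugs can have the primary event postponed, or lost when the routine diary stops at Day 8. Neither added sensitivity analysis (fever ignored; 37.8°C threshold) removes the adjustment, so nothing planned would show how much it drives the result. The trial's stated purpose is to establish an effect size on this endpoint.

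**Working it through.** **1. The plan's own figures.** Inputs from SAP 5.2: 63 and 38 evaluable subjects, difference 1.8 days, SD 3 days, two-sided 5%.
- SE = 3 × √(1/38 + 1/63) = 0.616; 1.8/0.616 = 2.92; normal-test power = Φ(2.92 − 1.96) = 83.2%.
- With Wilcoxon efficiency 3/π: Φ(2.92 × √0.955 − 1.96) = 81.4%. A simulated Wilcoxon test on normal data gives 81.6%. The stated 80% is reproduced.
- Enrolment: 63/0.9 = 70, 38/0.9 = 42.2, rounded up to 43; 70 + 70 + 43 = 183. Reproduced.
- Coding the masking rule with readings at 10:00 and 22:00 returns the SAP's worked answer of 34 h.

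**2. Count of Appendix 14.5.** There are 32 entries. Four have 0 h (electrolytes with glucose, glucose, sodium chloride, Trophamine), leaving 28 positive. Four entries correspond to the three drugs named in Protocol 5.9.3 (chlorphenamine twice, levodropropizine, paracetamol).

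**3. Average delay from one dose near recovery.** Readings are about 12 h (0.5 day) apart. For a dose at a random time relative to them, a window w masks w/12 readings on average, so delay = (w/12) × 0.5 day.
- Fluorometholone, 6 h: 0.25 day.
- Cefditoren or levofloxacin, 8 h: 0.33 day.
- Cefradine, 12 h: 0.5 day.
- Against 1.8 days this is 14% to 28%.

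**4. Repeated dosing at the SAP's default times.** The SAP uses 10:00 and 22:00 when diary times are missing, and 08:00 and 20:00 for incomplete twice-daily dose times. Each default reading then falls 2 h after a dose, inside even a 6 h window. Take study drug at 12:00 on Day 1 and all criteria truly met at the 22:00 reading on Day 2, which is 34 h. The courses are assumptions.

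| Drug and course | Start reading must be unmasked | Whole 24 h must be unmasked |
|---|---|---|
| Cefditoren, cefradine or fluorometholone twice daily, Days 2-4 | 94 h | 94 h |
| Same, Days 2-8 | no event, censored | no event, censored |
| Levofloxacin or fluorometholone once daily at 08:00, Days 2-4 | 34 h | 82 h |
| Same, Days 2-8 | 34 h | no event, censored |

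The 94 h is 10:00 on Day 5, the first reading after the course: 4 × 24 − 2. The shift is 60 h, or 2.5 days. The once-daily rows show that the choice between the two columns, which the SAP does not state, can decide the result. Clock times matter too. With readings at 07:00 and 19:00, before the same doses, the previous dose is 11 h old, so 6 h and 8 h windows have lapsed and only the 12 h window still masks.

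**5. Effect on power.** The documents give no usage rate, so 5-30% is assumed, equal in all arms (simulated Wilcoxon, 3,000 trials per cell, 38 v 63; a lost event is given the worst rank as a stand-in for censoring at the end of the diary).

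| Affected | +0.5 day | +2 days | +4 days | Event lost |
|---|---|---|---|---|
| 5% | 81% | 80% | 78% | 71% |
| 10% | 80% | 79% | 75% | 61% |
| 20% | 80% | 76% | 70% | 42% |
| 30% | 81% | 76% | 65% | 27% |

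**6. Unequal use, purely as a scenario.** With no drug effect, losing the event in 20% of placebo and 10% of active subjects gives rejection in 14% of trials, against 4.4% when both are 10%. Nothing in the documents says whether, or which way, use would differ.

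**The case against.** A reader might infer that every symptom-relief drug blocks both fever and all symptoms. The documents do not say so. The text is silent on the link, the only example is paracetamol on temperature, the protocol's sentence stands directly under the fever definition, and four entries carry 0 h. This stands: the fault is a missing link, open to different programming.

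A reader might also see the main damage in the seven entries of 24 h or more, such as "LEVOCETIRIZINE DIHYDROCHLORIDE" at 32 h. That is not supported either. These include antihistamines and anti-inflammatories, which may mask a listed symptom; Protocol 5.9.3 itself allows an antihistamine for symptom relief. Because the event is the later of symptoms and fever, a drug mapped to one symptom would still delay it after the fix. The clear case is confined to drugs acting on neither component, whose windows are 6 to 12 h.

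Nor do the documents support saying that the rule inflates the treatment effect. If placebo subjects took more relief drugs, false delay would fall on placebo, but ignoring real masking would favour placebo. No usage by arm is given.

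The blinded review may remove these drugs. It is a real safeguard, but it has no stated criterion and nothing obliges it to act. Ophthalmic use of fluorometholone is inferred from the route row in Appendix 14.3.2; Appendix 14.5 gives no route.

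**Conclusion.** The concern holds in a limited form and should be fixed before unblinding. As written, the rule and table can give wrong primary event times for recovered subjects taking one of four drugs with no evident masking effect. The individual consequence can be large, up to 2.5 days or loss of the event in the assumed courses, but it depends on repeated dosing and on readings that fall inside the window. At trial level the effect may be small: power stays at about 76-81% for delays of 0.5-2 days with equal use of 5-30%. Losses to 71% or 61% require 5% or 10% of subjects to lose the event altogether.

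The extra diary for suspected antibody-dependent enhancement would not rescue a recovered subject. It opens only if the investigator judges symptoms unresolved or worse by Day 8, or a new influenza-like illness develops later.

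**What to change.** Before unblinding:

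1. Add a column to Appendix 14.5, agreed blind, naming the component or components each drug can mask (temperature, each of the seven symptoms, or none). Enter none, 0 h, for antibiotics and any ophthalmic product. In SAP 10.1, apply each window only to those components.
2. State in SAP 10.1 whether masking applies to the reading that starts resolution or to every reading in the 24 h.
3. Add one sensitivity analysis of the primary endpoint with no medication adjustment, noting that it carries its own bias if drug use differs by arm.

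Separately, reconcile the Appendix 14.5 list with Protocol 5.9.3, which names three symptom-relief drugs.

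The cost is SAP wording, one blinded mapping of 32 entries and one extra table. The mapping needs clinical judgement, which is why it must be made blind.

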5.2 Determination of Sample Size

This study is designed to obtain effect sizes of 2 different CT-P27 treatment groups and placebo group based on the time from the administration of study drug to resolution of influenza symptoms and fever.

For this proof-of-concept dose-ranging study, assuming 90% of subjects are included in the eligible infected population, the total eligible sample size of 164 (63 eligible infected subjects per CT-P27 treatment groups and 38 subjects in placebo group) achieves 80% power to detect 1.8 days of reduction for the primary endpoint of time to resolution with 5% two-sided significance level and SD of 3 days using a Wilcoxon's rank-sum test.

Considering a dropout rate of 10%, this study will need 183 subjects to be enrolled to achieve 164 evaluable subjects.

For an effect size of 1.5 days of reduction in time to resolution with SD of 2.9 days, the total sample size could be increased to about 250 to achieve at least 80% statistical power with 5% two-sided significance level.

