8.2 Clinical Characteristics

The following continuous variables will be summarized using descriptive statistics by treatment group:

- Duration from onset of illness to study drug administration (hours): [Start date/time of study drug administration] – [Date/time of onset of illness]
- Influenza symptoms score at screening: Average scores of respiratory, constitutional, systemic and total symptoms
- Body temperature (°C) at screening

The following categorical variables will be summarized in contingency tables:

- Influenza subtype (Influenza A/H1, Influenza A/H3, Influenza A/H1 and H3, Unknown, NA)
- Influenza confirmed (by cell culture, qPCR, both, no)
- Rapid kit test results (positive, negative)

When influenza A virus load from qPCR has quantitative value or less than Lower Limit of Quantification (LLOQ), then influenza is confirmed. However, when influenza A virus load from cell culture has only quantitative value, then influenza is confirmed by cell culture.

Summary tables will be presented for ITT, ITTI, and PK populations. Also data will be listed for the ITT population.

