The primary efficacy endpoint will be analyzed using a Wilcoxon rank-sum test to assess differences between treatment groups (CT-P27 45 mg/kg vs placebo, CT-P27 90 mg/kg vs placebo), if every subject is followed until resolution of influenza symptoms and fever. The Wilcoxon rank-sum test will be used to test for a statistical significant difference of time to resolution between placebo and CT-P27. The results of the analysis will be summarized using p-values. The significant level will be set to 5%. If p-value is lower than 5%, it is considered that there is a significant difference between placebo and CT-P27. For subjects who withdrew from the study before the symptoms have resolved or if the symptoms did not resolve until the data cut-off, data will be censored at the latest date/time recorded on the diary or start date/time of study drug administration when there are no recorded data on the diary after study drug administration. If there is any censoring, the primary efficacy endpoint will be analyzed using Log-rank test and Gehans Wilcoxon test, and the result will be presented by p-values from the two tests. Also the table will present count of censoring reasons and 25th percentile, median, 75th percentile of time from administration of study drug to resolution. Kaplan-Meier plots will be presented.

CONFIDENTIAL

Statistical Analysis Plan

If there are no censoring data, sensitivity analysis using tipping point analysis under Missing Not at Random (MNAR) will be also performed to explain varying cases about average unobserved outcomes dropouts on two treatment groups.

Sensitivity Analyses which alter resolution conditions of primary efficacy analysis will be performed on the ITTI population. Following two endpoints will be assessed as described for the primary efficacy endpoint.

- Time (in days) to resolution of influenza symptom (respiratory and constitutional symptoms)

In the analysis, fever is not considered and the definition of resolution of symptom is the same as those of primary efficacy analysis.

- Time (in days) to resolution of influenza symptom and fever

In the analysis, threshold of resolution of fever is changed to 37.8°C and the definition of resolution of symptom is the same as those of primary efficacy analysis.

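### No covariate-adjusted or stratified analysis of the primary endpoint is planned, although relevant baseline values are already derived

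*SAP*

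**What the plan says.** SAP 10.1 compares each dose with placebo: "The primary efficacy endpoint will be analyzed using a Wilcoxon rank-sum test to assess differences between treatment groups". That test applies if everyone is followed to resolution. With any censoring, log-rank and Gehan-Wilcoxon tests replace it, reported as p-values with quartiles and Kaplan-Meier plots. No covariate or stratum is named on either route. The tipping-point analysis and the two added sensitivity analyses (symptoms only; fever threshold 37.8°C) are unadjusted too, as is Protocol 8.5.1.

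Randomisation is stratified by flu vaccination history and PK sub-study participation (SAP section 4).

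SAP 8.2 lists, for descriptive summary only, "Duration from onset of illness to study drug administration (hours"), "Influenza symptoms score at screening: Average scores of respiratory, constitutional, systemic and total symptoms", and screening body temperature.

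The sample size in SAP 5.2 rests on the unadjusted test. It is calculated "with 5% two-sided significance level and SD of 3 days using a Wilcoxon's rank-sum test". The design "achieves 80% power to detect 1.8 days of reduction for the primary endpoint of time to resolution", and the evaluable groups are "63 eligible infected subjects per CT-P27 treatment groups and 38 subjects in placebo group".

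**The concern.** The endpoint requires seven symptoms to be mild or absent and temperature to be below 37.0°C, each for 24 hours. Baseline symptom score and temperature are the starting values of those same components. Entry needs only two symptoms of moderate or greater intensity (Protocol 4.3.1), so starting points can differ widely.

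The clock starts at dosing, which may come up to 60 hours after onset. That window of 2.5 days is longer than the 1.8-day effect sought, so subjects enter at different stages of a self-limiting illness.

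None of these three variables is balanced by the stratified randomisation, and both doses share one placebo arm of about 38 evaluable subjects. If the variables are prognostic, an adjusted analysis would have more power and would account for chance imbalance. SAP 1.1 says the data are meant to establish an effect size for later studies, yet SAP 10.1 yields no treatment-effect estimate, adjusted or not.

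**Working it through.** **Inputs from SAP 5.2:** 63 and 38 evaluable per comparison, difference 1.8 days, SD 3 days, two-sided 5%. These counts are already net of dropout: "Considering a dropout rate of 10%, this study will need 183 subjects to be enrolled to achieve 164 evaluable subjects", and 164/0.9 = 182.2, rounded up to 183. A calculation that starts from 63 and 38 should not remove 10% again.

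**Step 1: reproduce the stated power.** The rank-sum test has efficiency 3/π = 0.955 relative to the t-test for normal data.

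- SE = 3 × √[(1/38 + 1/63)/0.955] = 0.631 days.
- Power = Φ(1.8/0.631 − 1.96) = Φ(0.894) = 81.4%.
- Noether's formula: p = Φ(1.8/(3√2)) = 0.664. Power = Φ(√(12 × 101 × 0.376 × 0.624) × 0.164 − 1.96) = 79.1%.
- Noncentral t with the same efficiency: 80.7%. Simulated rank-sum test on normal data (10,000 runs): 80.6%.

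The stated 80% is reproduced.

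**Step 2: effect of adjustment.** The documents give no R² for the covariates, so it is assumed. In closed form the residual SD becomes 3√(1 − R²). At R² = 0.10, SE = 0.631 × √0.90 = 0.598 and power = Φ(1.8/0.598 − 1.96) = 85.3%. The smallest difference detectable with 80% power is (1.960 + 0.842) × SE.

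The censored route was simulated with 2,000 runs per row. Assumptions: gamma times with placebo mean 6 days and SD 3 in both arms, a 1.8-day reduction, R² on the underlying normal scale, and censoring at 7 days (about 22% censored). Rank ANCOVA used 4,000 runs on normal data. Its unadjusted comparator stayed near 80 to 81%.

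| R² (assumed) | Closed-form power | Detectable difference (days) | Rank ANCOVA | Log-rank | Adjusted Cox |
|---|---|---|---|---|---|
| 0 | 81.4% | 1.77 | 80.1% | 78.55% | 78.95% |
| 0.05 | 83.4% | 1.72 | 81.8% | not run | not run |
| 0.10 | 85.3% | 1.68 | 83.9% | 78.70% | 82.05% |
| 0.20 | 89.1% | 1.58 | 87.0% | 78.95% | 88.40% |
| 0.30 | 92.7% | 1.48 | 91.3% | 79.60% | 92.75% |

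Log-rank power does not depend on R² here, so the four log-rank results can be averaged: 78.95%. The Cox gains over that figure are 3.1, 9.5 and 13.8 points at R² 0.10, 0.20 and 0.30. A separate simulation of the same two tests, with lower starting power, gave 71 vs 75%, 73 vs 81% and 73 vs 85%. Those are gains of 4, 8 and 12 points, with no gain at R² 0 to 0.05.

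**Step 3: precision and type I error.** The mean standard error of the log hazard ratio was 0.241 to 0.242 unadjusted and 0.243 to 0.248 adjusted. Power rises because the conditional hazard ratio lies further from 1, not because its standard error falls. Under no effect, the adjusted Cox Wald test rejected in 4.9 to 6.5% of runs and the log-rank test in 4.45 to 5.8%. The Wald test is slightly liberal at this size, and a little of its gain comes from that.

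**Step 4: chance imbalance.** The standardised difference in one covariate between 38 and 63 subjects has SE √(1/38 + 1/63) = 0.205. A difference of at least 0.3 SD occurs with probability 2 × [1 − Φ(0.3/0.205)], about 14%. At an assumed R² of 0.20 it would shift a difference in means by √0.20 × 3 × 0.3 = 0.40 days, or 22% of 1.8.

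**Step 5: scale for one covariate.** Assume the dosing delay is uniform and unrelated to total illness length. Its SD is then 2/√12 = 0.58 days (0 to 48 h) or 2.5/√12 = 0.72 days (0 to 60 h). Squared and divided by 3² = 9, that is an R² of 0.04 to 0.06 from delay alone.

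**The case against.** The planned tests are valid under randomisation, and chance imbalance is already covered by their type I error. The power target was set for an unadjusted test and is met. A reader might infer that the trial falls short of its promised power; Step 1 shows that it does not. A reader might also infer that precision is lost. The plan reports no effect estimate or interval that could be wider than necessary, and Cox adjustment does not reduce the standard error of the log hazard ratio. Both objections stand.

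The size of the gain is assumed. Eligibility narrows the covariate range, which probably limits R². The 7-day cut is also an assumption: SAP 10.1 uses diary records from the suspicious-ADE assessment, so follow-up can run longer for some subjects. The Gehan-Wilcoxon test was not simulated. These points limit the figures, not the direction of the gain if the covariates are prognostic.

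Replacing the primary test with a Cox model would be hard to defend. It would change a protocol-specified test, bring in proportional hazards and leave the uncensored route untouched. Screening temperature is a weak covariate, because inclusion criterion 5 admits subjects with recent fever who took an antipyretic in the previous 6 hours. The Domain 1 total score includes items outside the endpoint, such as neck pain, interrupted sleep and loss of appetite. These objections shape the fix. They do not explain why no adjusted analysis is planned at all.

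**Conclusion.** The point holds as a missed opportunity, not as an error. Both routes in SAP 10.1 ignore baseline covariates and the randomisation strata, and no sensitivity analysis makes up for it. The power forgone on the log-rank route is about nothing at R² 0 to 0.05, 3 to 4 points at 0.10, 8 to 9 at 0.20 and 12 to 14 at 0.30. All of these rest on an R² that the documents do not give and on the simulation assumptions above. The documents do not support saying that the trial is underpowered for lack of adjustment, that its intervals are too wide, or that its planned tests are invalid. The stronger reason to act is that the trial sets out to obtain an effect size and plans no estimate that accounts for baseline differences.

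**What to change.** Keep the planned tests. Before unblinding for the first analysis, add to SAP 10.1 one prespecified analysis of each dose against placebo, run whether or not there is censoring. For example, use a Cox model that is:

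- stratified by, or adjusted for, flu vaccination history and PK sub-study participation;
- adjusted for the baseline symptom score over the seven endpoint items and for hours from onset to dosing;
- optionally adjusted for screening temperature, given possible masking by antipyretics.

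Report the adjusted effect estimate with a 95% confidence interval, and state a rule for missing baseline values.

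The cost is SAP text, a few lines of code and one more table, with no new data. The hazard ratio will be conditional on the covariates and assumes proportional hazards; the SAP should say so. The addition must be recorded in SAP section 13, which already lists added sensitivity analyses of the primary endpoint. Protocol 8.3 allows such changes in the SAP before database lock and unblinding.
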